7.3.2 Adverse Event Information

AEs with missing relationship will be considered 'Related' for summary purposes but recorded as missing in the listings.

7.4 Study Deliveries

7.4.1 Early Stopping

In the event that some or all of the cohorts stop the study early, it may be decided to make a single delivery for all study cohorts with reduced number of TFLs.

7.4.2 Purpose of Study Deliveries

Interim safety and efficacy analyses may be performed throughout the life cycle of the study as required for ongoing evaluation of the risk benefit profile of EDP1815. These may include either all participants enrolled in the study or use a subset of participants who transitioned to this study from a specific parent study or a specific parent study cohort. Analyses performed once participants from a specific parent study or a specific parent study cohort complete 208 study will be considered as final deliveries.

All analyses will also incorporate data collected on the parent atopic dermatitis EDP1815 studies which feed into this study.

7.4.3 Planned Schedule of Deliveries

The interim and final analyses will be performed throughout the life cycle of the study as required.

At a minimum, there will be EDP1815-207 parent-study specific analysis performed after all participants from

- 207 cohorts 1-3 (Delivery 1)
- 207 cohort 4 (Delivery 2)

have completed this study.

Analysis will be restricted to participants from the corresponding cohorts in the parent study who transitioned to this study.

7.4.4 Endpoints to be Included in the Study Deliveries

All endpoints will be included into the parent-study specific analyses.

7.4.5 Adjustment of Confidence Intervals and p-values

No inferential comparisons of efficacy will be performed so no adjustments for alpha-spending are required.

7.4.6 Practical Measures to Minimise Bias

This is an OLE study with all participants taking EDP1815 capsules so no blinding is required for the study medication in this study. However, investigators and participants will continue to be blinded to the participant's treatment assignment in the parent study in order to minimize bias.

Unblinded results will not be shared with any study site staff or participants.

7.4.7 Documentation of Study Deliveries

The study is open label but the [REDACTED] team will be unblinded to the treatment assignment only from the time of parent study DBL.

As the patients' assignments data will be only available for [REDACTED] after the parent study DBL, there is no risk of unblinding and there will be no separate unblinded team. Any interim analysis data will be held in the non-restricted file structure available to the whole [REDACTED] team working on 208 study.

7.5 Multi-centre Studies

Results will be presented for all centres combined.

7.6 Multiple Testing

The focus of this study is on safety, specifically the incidence and rate of TEAEs per 100-patient years, and as such no adjustments will be made for multiple testing in this study.

7.7 Visit Windows

All data will be reported according to nominal visits. For example, if a Week 4 visit occurred on Day 30 instead of the nominally expected Day 28 it will be reported and included in the summary statistics/statistical analyses for Week 4.

Scheduled visits which occur outside the protocol-specified visit window (e.g., if the Week 4 visit occurred on Day 32, outside of the Day 25-31 window), this will be noted as a protocol deviation but data collected will still be included in all summary and analysis tables.

Unscheduled visits and Early Termination visit will not be included in summary or analysis tables, unless they are baseline measurements or provide data towards a safety endpoint which looks at worst-case post-baseline.

All listings will include all collected data even if they are from an unscheduled visit.

8 Summary of Study Data

All continuous variables will be summarized using the following descriptive statistics: n (non-missing sample size), mean, SD, median, maximum, and minimum. The frequency and percentages (based on the non-missing sample size) of observed levels will be reported for all categorical measures.

In general, all data will be listed, sorted by group (1, 2, and 3), country, site number and participant number. Relevant listings will include whether the assessment was performed and the date, study day/visit and time of the assessment as applicable.

Any study population or safety tables, listings or figures that display treatment will always present the actual treatment received rather than the planned treatment as the primary objective is to evaluate the safety of EDP1815. For efficacy summaries planned treatment will be used.

Unless otherwise specified below, all summary tables will be structured with a column for each group (groups 1 and 2 will be presented in 207 cohorts 1-3 delivery and group 3 will be presented in 207 cohort 4 delivery) and an additional 'Total' column which contains all patients included in the relevant interim or final analysis.

The labels presented for each group will be as follows:

- Group 1 = 1.6×10^{11} TCPD
- Group 2 = 6.4×10^{11} TCPD
- Group 3 = 8.0×10^{10} TCPD

For summaries of safety endpoints that look at the period defined since first dose of active IMP either in this study or the relevant parent study, the data will be ordered and labelled as follows:

- 1.6×10^{11} TCPD (For 207 cohorts 1-3 delivery only)
- 6.4×10^{11} TCPD (For 207 cohorts 1-3 delivery only)

- 6.4×10^{11} TCPD to 1.6×10^{11} TCPD (For 207 cohorts 1-3 delivery only)
- 8.0×10^{10} TCPD (For 207 cohort 4 delivery only)
- Total

For efficacy outputs, columns will be ordered and labelled as follows:

- For 207 cohorts 1-3 delivery:
 - 1.6×10^{11} TCPD in this study, Placebo in the parent study
 - 1.6×10^{11} TCPD in this study, 1.6×10^{11} TCPD in the parent study
 - 1.6×10^{11} TCPD in this study, 6.4×10^{11} TCPD in the parent study
 - 6.4×10^{11} TCPD in this study, Placebo in parent study
 - 6.4×10^{11} TCPD in this study, 6.4×10^{11} TCPD in the parent study
 - Total
- For 207 cohort 4 delivery:
 - 8.0×10^{10} TCPD in this study, Placebo in the parent study
 - 8.0×10^{10} TCPD in this study, 8.0×10^{10} TCPD in the parent study
 - Total

For the analysis:

- For study disposition summaries where it is appropriate to report information on participants that have failed screening, the enrolled population will be used.
- For the primary estimands around adverse events, together with estimands based on efficacy count endpoints looking into the use of rescue medications, the FAS will be used along with DPS1 and DPS2.
- For the responder efficacy endpoints the FAS along with DPS4b will be used
- For supplementary estimands for the key efficacy responder endpoints the FAS along with DPS4 and DPS4a will be used.
- For continuous endpoints the FAS along with DPS4a will be used.
- For safety endpoints where data is collected at specific timepoints the FAS along with DPS3 and DPS4 will be used.

8.1 Early Stopping

In the event that the study is stopped early and only a reduced amount of outputs are needed, the following will be presented:

- Completion/withdrawal from the study/treatment will be summarised and listed (per Section 8.2)
- The number and percentage of participants enrolled within each region, country and site will be summarized (per Section 8.2)
- Demography data of age, sex, race, and ethnicity will be summarized and listed (per Section 8.4)

Data will be presented as collected, no imputations or data exclusion will be made.

The list of outputs produced in the case the study is stopped early are provided in 16Appendix 1: List of Tables, Figures and Listings.

8.2 Study Disposition

Completion/withdrawal from the study and completion/discontinuation from treatment, together with reasons for withdrawal from the study or discontinuation from treatment will be listed and the following will also be tabulated:

- Number and percentage of participants who completed the study
- Number and percentage of participants withdrawn from the study and the reported reason for withdrawal
- Number and percentage of participants who completed the 36-week treatment period
- Number and percentage of participants who discontinued treatment early and reason for discontinuation

For participants who fail to meet the eligibility criteria the reasons for failure, including the inclusion/exclusion criteria that were not met will be summarized and listed.

The number and percentage of participants enrolled within each region, country and site will be summarized.

For the enrolled population, the number and percentage of participants in each analysis population will be presented. Inclusion/exclusion in each study population will also be listed, together with reasons for exclusion.

The number and percentage of participants with data available for each scheduled visit (including the early termination visit) will be summarized.

Missed visits due to COVID-19 will also be summarized and listed.

8.3 Protocol Deviations

The number and percentage of participants in the full analysis population with at least one significant protocol deviation will be summarized by deviation category.

All protocol deviations will also be listed.

8.4 Demographic and Baseline Variables

Demography data of age, sex, race, and ethnicity will be summarized and listed together with height, weight, and BMI at the parent study baseline.

8.5 Medical History

Medical history and concurrent illnesses will be captured and coded using the Medical Dictionary for Regulatory Activities (MedDRA®). The dictionary will be updated through the life of the study with version 24.0 used initially.

Parent study medical history will be used in the summaries together with 208 data to present all past and concurrent medical history. Parent study medical history won't be recoded if the MedDRA will be updated through the life of 208 study, the dictionary from the time of the parent study data base lock will be used.

Concurrent illnesses and medical conditions will be classified as 'current' if the end date is on or after the date of first dose of study drug, or the condition has been marked as ongoing. Otherwise, they will be classified as 'past'.

Past and current medical history will be summarized separately by System Organ Class (SOC) and Preferred Term (PT). Summary tables will contain the number and percentage of patients. A patient who has multiple conditions in the same SOC or with the same PT will be counted only once in the patient counts. Medical history summaries will be sorted by the internationally agreed SOC order (Table 10) and decreasing frequency of PT within SOC in the Total column.

All medical history data will be listed.

8.6 Prior and Concomitant Medications

Medications collected during the 208 study will be coded according to the World Health Organization Drug Dictionary (WHODD). The dictionary will be updated through the life of the study with the version dated 01Mar2021 used initially. Medical procedures will not be coded.

Parent study medications data will be used in the summaries together with 208 data to present all prior and concomitant medications from the whole period before and during 208 study. Parent study medications won't be recoded if the dictionary will be updated through the life of 208 study, the dictionary from the time of the parent study data base lock will be used.

Concomitant medications are defined as any medications taken during the 208 treatment period or follow-up period after treatment. This includes any medications started before the 208 first dose and ongoing after the first dose. Prior medications are defined as any medication taken before or during the parent study which were stopped before the first dose of 208 study medication.

Missing and partial start and stop dates will be imputed using the rules specified in [Section 7.3.1](#) before classifying therapies as prior or concomitant. If the classification is still ambiguous after missing and partial dates have been imputed, then the medication will be considered concomitant.

Medications will be summarized by WHODD Anatomical Main Group (Level 1), Therapeutic Subgroup (Level 2) and preferred term. The summaries will report incidence within each relevant level so that

a participant taking multiple medications coded to the same relevant Level 1, Level 2 or preferred term would only be counted once within the incidence count for that level or term.

Separate summaries will be produced for each of the following:

- All concomitant medications
- Concomitant medications started before or during the parent study
- Concomitant medications started during the 208 treatment period
- Concomitant medications started during the 208 follow-up period

All prior and concomitant medications will be listed.

Categorization of all concomitant medications prescribed during the study will be done by Evelo clinician in order to identify TCS/TCI rescue therapy, antimicrobial rescue therapy and prohibited medications.

8.7 Treatment Compliance

Treatment compliance will be summarized for the whole 36-week treatment period.

Summary statistics (n, mean, SD, median and range) will be produced together with the number and percentage of participants within each of the categories defined in [Section 5.3.2.1](#). Percentages will use the number of participants who started the treatment period as the denominator.

Data from the dosing log and the calculated treatment compliance will also be listed.

8.8 Emollient Compliance

Emollient compliance will be summarized for the whole treatment and follow-up periods.

Summary statistics (n, mean, SD, median and range) will be produced together with the number and percentage of participants within each of the categories defined in [Section 5.3.2.2](#). Percentages will use the number of participants who started the period as the denominator.

Data from the daily diary and the calculated emollient compliance will also be listed.

9 Primary Safety Analysis

9.1 Early Stopping

In the event that the study is stopped early and only a reduced amount of outputs are needed, safety data will only be reported for the period beginning with the first dose of active IMP in this study. Only incidence and number of events will be presented for the following categories:

- TEAEs
- Serious TEAEs

Data will be presented as collected, no imputations or data exclusion will be made.

The list of outputs produced in the case the study is stopped early are provided in 16Appendix 1: List of Tables, Figures and Listings.

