3. STUDY VARIABLES

3.1. Safety Variable(s)

3.1.1. Primary Safety Variable(s)

The primary safety variables will be the incidence and rate per 100 patient-years of TEAEs. Both the period defined by this study alone and the period defined by this study and the relevant parent study will be reported.

Subgroups of TEAEs will be evaluated as follows:

- All TEAEs
- TEAEs of Grade 2 or above
- TEAEs of Grade 3 or above
- Serious TEAEs
- Fatal TEAEs
- TEAEs causing discontinuation of study drug

- Study drug related TEAEs Study (defined by an investigator assessment of possible, probable, or definite relationship to IMP)
- Study drug related TEAEs of Grade 2 or above
- Study drug related TEAEs of Grade 3 or above
- Study drug related serious TEAEs
- Study drug related fatal TEAEs
- Study drug related TEAEs causing discontinuation of study drug

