4.2 Endpoints

The primary endpoints for the study are:

- The incidence and rate per 100 patient-years of treatment-emergent adverse events during the 36-week treatment and 4-week follow-up period
- The incidence and rate per 100 patient-years of treatment-emergent adverse events during the treatment period of this study and the relevant parent study

The secondary efficacy endpoints for the study will be evaluated at all scheduled visits (unless otherwise specified), with measures involving changes from baseline using the baseline assessment from the relevant EDP1815 parent study. The secondary endpoints are as follows:

- Percentage of participants achieving Eczema Area and Severity Index (EASI)-50
- Percentage of participants achieving EASI-75

- Percentage of participants achieving EASI-90
- Mean absolute change and percentage change from baseline in EASI Score
- Percentage of participants achieving Validated Investigator's Global Assessment (vIGA) of 0 or 1 with a ≥ 2 -point improvement from baseline
- Percentage of participants achieving vIGA of 0 or 1
- Percentage of participants achieving vIGA of 0
- Mean absolute change and percentage change from baseline in vIGA*BSA (BSA=body surface area)
- Mean absolute change and percentage change from baseline in BSA
- Percentage of participants achieving BSA-50
- Percentage of participants achieving BSA-75
- Percentage of participants achieving BSA reduction to 3% BSA or less
- Mean absolute change and percentage change from baseline in SCORing Atopic Dermatitis (SCORAD) score
- Percentage of participants achieving SCORAD-35
- Percentage of participants achieving SCORAD-50
- Percentage of participants achieving SCORAD-75
- Mean absolute change and percentage change from baseline in Dermatology Life Quality Index (DLQI) score
- Percentage of Participants achieving a reduction of ≥ 4 in the DLQI score, of those with a score of ≥ 4 at baseline
- Mean absolute change from baseline in Peak Pruritus Numerical Rating Scale (PP-NRS) score
- Percentage of participants achieving a reduction of ≥ 2 in the PP-NRS, of those with a score of ≥ 2 at baseline
- Percentage of participants achieving a reduction of ≥ 4 in the PP-NRS, of those with a score of ≥ 4 at baseline
- Mean absolute change from baseline in Sleep Disturbance Rating Scale (SD-NRS) score
- Percentage of participants achieving a reduction of ≥ 2 in SD-NRS score, of those with a score of ≥ 2 at baseline

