7.1.2.2 Data Point Set 2 (DPS2)

DPS2 consists of all observed data collected following the first dose of active IMP, either in the parent study or in this study until 30 days after the last dose of IMP in this study.

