V4.0	Removed endpoints for worst-case change from baseline with respect to values outside the normal ranges for vital signs and ECG parameters	Worst-case change from baseline with respect to values outside the normal ranges for vital signs, ECG parameters and clinical laboratory parameters for given as secondary safety endpoint but only changes with respect to normal ranges were summarized for the lab parameters. For ECG and vital signs, it was felt that only changes from PCI criteria were of specific interest.
V4.0	Efficacy outputs will not be produced as planned	The study was early terminated after the parent study primary endpoint was not met.
V4.0	Only reduced amount of disposition, demography and safety data will be summarised and listed	The study was early terminated after the parent study primary endpoint was not met.

15 Bibliography

16 Appendix 1: List of Tables, Figures and Listings

All outputs detailed in the following sections will be produced for the final analysis. In addition, those which will be produced for the interim analysis are flagged in the 'Interim' column.

If the study is stopped early, outputs will be produced as specified in the Early Stop column.

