16.3.1 Tables

Number	Title	Population	Data Point Set	Early Stop	Programming notes for Early Stop
14.3.1.1.1	Overview of TEAEs reported in 208	FAS	DPS1	Yes	New number 14.3.1.1
14.3.1.1.2	Overview of TEAEs reported since first active dose in 207 or 208	FAS	DPS2	No	

Number	Title	Population	Data Point Set	Early Stop	Programming notes for Early Stop
14.3.1.2.1	Summary of the Incidence and Rate per 100 Patient-Years of TEAEs by System Organ Class and Preferred Term	FAS	DPS1	Yes	New number 14.3.1.2 Only present E (number of events); exclude rate
14.3.1.2.2	Summary of the Incidence and Rate per 100 Patient-Years of TEAEs by System Organ Class and Preferred Term	FAS	DPS2	No	
14.3.1.3.1	Summary of the Incidence and Rate per 100 Patient-Years of TEAEs of Grade 2 or Above by System Organ Class and Preferred Term	FAS	DPS1	No	
14.3.1.3.2	Summary of the Incidence and Rate per 100 Patient-Years of TEAEs of Grade 2 or Above by System Organ Class and Preferred Term	FAS	DPS2	No	
14.3.1.4.1	Summary of the Incidence and Rate per 100 Patient-Years of TEAEs of Grade 3 or Above by System Organ Class and Preferred Term	FAS	DPS1	No	
14.3.1.4.2	Summary of the Incidence and Rate per 100 Patient-Years of TEAEs of Grade 3 or Above by System Organ Class and Preferred Term	FAS	DPS2	No	
14.3.1.5.1	Summary of the Incidence and Rate per 100 Patient-Years of Serious TEAEs by System Organ Class and Preferred Term	FAS	DPS1	Yes	New number 14.3.1.4 Only present E (number of events); exclude rate
14.3.1.5.2	Summary of the Incidence and Rate per 100 Patient-Years of Serious TEAEs by System Organ Class and Preferred Term	FAS	DPS2	No	

Number	Title	Population	Data Point Set	Early Stop	Programming notes for Early Stop
14.3.1.6.1	Summary of the Incidence and Rate per 100 Patient-Years of Fatal TEAEs by System Organ Class and Preferred Term	FAS	DPS1	No	
14.3.1.6.2	Summary of the Incidence and Rate per 100 Patient-Years of Fatal TEAEs by System Organ Class and Preferred Term	FAS	DPS2	No	
14.3.1.7.1	Summary of the Incidence and Rate per 100 Patient-Years of TEAEs Causing Discontinuation of Study Drug by System Organ Class and Preferred Term	FAS	DPS1	No	
14.3.1.7.2	Summary of the Incidence and Rate per 100 Patient-Years of TEAEs Causing Discontinuation of Study Drug by System Organ Class and Preferred Term	FAS	DPS2	No	
14.3.1.8.1	Summary of the Incidence and Rate per 100 Patient-Years of Study Drug Related TEAEs by System Organ Class and Preferred Term	FAS	DPS1	No	

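### On early stop the SAP drops the second primary safety period (TEAEs since first active dose across 207 and 208) from the 208 outputs, and its table of changes does not say so

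*SAP*

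**What the plan says.** **Two primary periods.** SAP 4.2 lists first "The incidence and rate per 100 patient-years of treatment-emergent adverse events during the 36-week treatment and 4-week follow-up period", and second "The incidence and rate per 100 patient-years of treatment-emergent adverse events during the treatment period of this study and the relevant parent study". Protocol 3.1.1 commits to the pair: "Both the period defined by this study alone and the period defined by this study and the relevant parent study will be reported". Protocol 2.1 and 11.3.1 and SAP 9.2 also carry both. SAP 9.2.1 assigns data point set DPS1 to the 208-only period and DPS2 to the combined period. For the combined period its summary measure is the rate per 100 patient-years by treatment group. SAP 7.1.2.2 fixes where that clock starts: "DPS2 consists of all observed data collected following the first dose of active IMP, either in the parent study or in this study".

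**Early stop.** SAP 9.1 applies when the study stops early and reduced outputs are needed. It states that "safety data will only be reported for the period beginning with the first dose of active IMP in this study", and limits the content to incidence and event counts for TEAEs and serious TEAEs. SAP 11.1 repeats the limit on the period. In SAP 16.3.1 the combined-period overview, Table 14.3.1.1.2 ("Overview of TEAEs reported since first active dose in 207 or 208"), is marked Early Stop = No.

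**Statements pointing the other way.** The introduction to SAP 16.3 says that an early stop leaves the safety outputs as planned. SAP 7.4.2 says: "All analyses will also incorporate data collected on the parent atopic dermatitis EDP1815 studies which feed into this study".

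**Disclosure.** SAP Section 14, Table 9 gives the reason for reduced reporting: "The study was early terminated after the parent study primary endpoint was not met". Its last two rows say that efficacy outputs will not be produced as planned and that disposition, demography and safety output is reduced. Neither row mentions a primary period.

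**The concern.** The primary objective is long-term safety. SAP 11.2 plans exposure categories up to 52 weeks across the two studies, whereas planned treatment in 208 alone is 36 weeks. An early stop can only shorten 208 for people still on treatment, so the combined period matters more in exactly the case where it is removed.

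There is also a question of transparency. Table 9 records smaller changes one by one, such as the renaming of an intercurrent-event strategy and the addition of SCORAD-35. A reader who relies on it would not learn that one of two protocol-stated primary periods has gone. A programmer would find that 9.1, 11.1 and the Early Stop column say one thing and 16.3 says another.

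**Working it through.** The documents give no sample size, event rate or exposure figure on this point, so there is no stated figure to reproduce. The check is a table count, a search for substitutes and simple exposure arithmetic.

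**1. Count of adverse-event summary tables (SAP 16.3.1, 14.3.1.1.1 to 14.3.1.14.2).**

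| Data point set | Planned | Kept on early stop |
|---|---|---|
| DPS1 (208 only) | 14 | 4 (14.3.1.1.1, 14.3.1.2.1, 14.3.1.5.1, 14.3.1.14.1) |
| DPS2 (since first active dose) | 14 | 0 |

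The second primary period therefore has no retained summary.

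**2. Is there a substitute?** The one retained adverse-event listing (16.2.7.1.1) is assigned DPS5, which SAP 7.1.2.7 starts at the first dose in 208. On that definition it does not carry 207 events either.

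**3. Has the rule been applied?** SAP 9.1 is conditional, but Table 9 records both the early termination and the reduced output.

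**4. Exposure outside the retained window, per participant.** Inputs: 16 weeks of treatment in 207 (Protocol 4.1, SAP 5.1) and w weeks of treatment in 208, ignoring any gap between the studies. For someone on active drug in both studies, the share left out is 16/(16+w):

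- w = 8: 16/24 = 67%
- w = 12: 16/28 = 57%
- w = 24: 16/40 = 40%
- w = 36: 16/52 = 31%

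**5. The same across all participants.** Let f be the share of 208 participants who were on active drug in 207. The documents do not give f, so I assume 0.50 to 0.75. With everyone treated for w weeks in 208, the share of all active exposure left out is 16f/(16f+w):

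| w | f = 0.50 | f = 0.75 |
|---|---|---|
| 8 | 8/16 = 50% | 12/20 = 60% |
| 12 | 8/20 = 40% | 12/24 = 50% |
| 24 | 8/32 = 25% | 12/36 = 33% |
| 36 | 8/44 = 18% | 12/48 = 25% |

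**6. Would restoring the table be enough?** No. The DPS2 measure is a rate, but 9.1 allows only incidence and counts, in 2 of the 12 TEAE categories listed in 9.2. If only the period limit were lifted, the table would give crude counts that pool people followed for about 16+w weeks with people followed for w weeks.

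**The case against.** The strongest reply is that this is a declared choice in a terminated, purely descriptive study. SAP 7.4.1 allows a reduced set of outputs, 9.1 and 11.1 name the period kept, and Appendix 1 flags each table. On that reading 7.4.2 is not breached, because the early-stop provision is an exception to it. The Protocol Summary also names only the 208 treatment and follow-up period as primary, and that is the period kept. Much of this stands: the rule can be found in the SAP. It does not explain why Table 9 omits the loss or why 16.3 says the opposite. The body of the protocol and SAP 4.2 both treat the combined period as primary.

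A second reply is selection. Entry to 208 required completing 207 treatment and satisfactory compliance (Protocol 5.1), and participation was elective (Protocol 4.3). The 207 part of the combined period therefore comes only from completers. This stands, and it affects every row of the table. It is a reason to label the table, since the same limitation was built into the planned endpoint.

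Three stronger readings are tempting, and the documents do not support them:

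- *Early stop causes new starters to be pooled with continuing participants.* The 208-only columns are by 208 dose under the full plan too (Protocol 11.3.1, SAP Section 8). The DPS2 columns also pool former placebo with continuing participants. DPS2 aligns the clock to first active dose but does not separate the two groups.
- *No retained table counts from first exposure.* For former placebo participants, DPS1 does start at their first EDP1815 dose. The statement is true only for those already on active drug in 207.
- *The 207 exposure goes unreported.* The documents show only that it is absent from the 208 outputs. 207 is a controlled study with its own database lock, and how its report covers these events cannot be judged from here. Such a report would still not supply the continuous 207-to-208 period.

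**Conclusion.** The point holds for the 208 outputs. With early termination in effect, the second primary period has no retained table (0 of 14), Table 9 does not disclose this, and 16.3 contradicts 9.1, 11.1 and the Early Stop column. For a participant on active drug throughout, between 31% (w = 36) and 67% (w = 8) of continuous exposure falls outside the retained window. These figures rest on a full 16 weeks in 207 and on illustrative values of w. The documents do not say how long participants were treated in 208 before termination, and some may have completed 36 weeks, so a reader should not infer that the retained window is necessarily short. The all-participant range also depends on the assumed share on active drug in 207. No inferential result is affected, because the study has none. What is lost is a protocol-stated descriptive primary endpoint.

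**What to change.** 1. Set Early Stop = Yes for Table 14.3.1.1.2.
2. Amend SAP 9.1 and 11.1 so that this table is exempt from the 208-only limit and from 9.1's restriction to incidence and counts in two categories. Present number of events, patient-years and rate per 100 patient-years, using the active-exposure duration already defined in SAP 5.3.4.1.
3. Label the whole table as restricted to participants who completed 207 treatment and entered 208. Add a note that its 207 portion is selected, especially for the discontinuation and fatal rows.
4. Reconcile the introduction to SAP 16.3 with 9.1, 11.1 and the Early Stop column.
5. If the sponsor still drops the period, state in Table 9 that the second primary endpoint is not reported, and why.

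The cost is one already-specified table and a little programming beyond the reduced package. SAP 7.4.7 indicates that 207 allocation is available after the parent database lock. The fallback in item 5 costs one sentence.
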